In the study, an observational clinical study strategy will be followed in routine spinal anesthesia applications. Applications will be made to the Erciyes University Ethics Committee. Patients will be informed before the procedure begins, and their written consent will be obtained. The study will be conducted from May 2025 to December 2025. ASA III and IV, preeclampsia, cardiorespiratory problems, pregnancy or pre-existing diabetes, intrauterine growth restriction, and fetal abnormalities, abruptio placentae, placenta previa, placenta accreta or percreta, pregnant women who are in an emergency situation and unwilling to participate, those with contraindications to spinal anesthesia, those weighing <50 kg or >110 kg, and those taller than 170 cm or shorter than 150 cm will not be included in the study. There was no pre-planning among the patients. The patient will undergo standard monitoring, including non-invasive blood pressure, ECG, and pulse oximetry, with baseline blood pressure and heart rate measurements recorded. Two 20-G intravenous cannulas will be inserted, and an IV balanced solution will be administered using these routes. Vertebral body length (VBL) measurements are determined by measuring from the midpoint of C7 to the Tuffier line. To test this hypothesis, a 0.5% heavy bupivacaine dose will be calculated as $0.2 \text{ mg} \times (\text{vertebral body length} = \text{distance between C7 and Tuffier's line}) \text{ cm}$. In our clinic, all three dose calculation systems are routinely used in spinal anesthesia for cesarean sections. As is routinely done, after skin infiltration with lidocaine, a 25-G short bevel Quincke spinal needle will be inserted into the L3-4 vertebral space while the patient is in a sitting position. After cerebrospinal fluid aspiration, the calculated dose of bupivacaine will be administered over 5 seconds. The patient and evaluator group assignments will be unknown. The data of 285 patients who underwent routine procedures will be examined, and the results will be separated based on the dose of bupivacaine administered to the pregnant woman. According to the results, the data is as follows: Patients in the VBU Group (thoracolumbar vertebral length between C7 and the Tuffier line) received $0.2 \text{ mg} \times \text{VBU cm}$ of 0.5% hyperbaric bupivacaine, while patients in the Height Group (calculated dose) received a volume of 0.5% hyperbaric bupivacaine based on a height-adjusted dose of 0.065 mg/cm height, calculated according to the patient's height. The AD Group (adjusted dosage) will receive intrathecal heavy bupivacaine (0.5%) as determined by Harten's dosage chart, adjusted for the patient's height and weight (Table 1) [11].

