
Postoperative analgesia will be performed bilaterally with a transverse abdominis plane block using 20 ml of 0.25% bupivacaine. The upper sensory level of anesthesia will be systematically assessed by measuring the loss of needle-prick sensation in the midclavicular line at 2-minute intervals. Additionally, the time to surgical incision, the sensory block level at the thirty-minute mark, the performance of the head-down tilt, the administration of additional analgesia, and the transition to general anesthesia will be recorded. Mean arterial blood pressure and heart rate will be recorded initially and then at 3-minute intervals starting 3 minutes after spinal injection and continuing until the end of the surgical procedures. The onset of nausea and vomiting will be systematically recorded along with the amount of ephedrine administered. A nurse present during delivery who is unaware of the patient's assigned group will assess the Apgar scores both 1 minute

Clinical Management

As per routine practice, patients will be immediately placed in the supine position with a 15-degree left lateral tilt. All patients will receive supplemental oxygen via a nasal cannula. Bradycardia (defined as a heart rate < 60 beats/min) will be treated with 0.5 mg of intravenous atropine. Hypotension, defined as a decrease in baseline systolic blood pressure of more than 30% or a systolic blood pressure below 90 mmHg, will be managed with 5 mg of intravenous ephedrine. In instances of dizziness, nausea, or vomiting, 5 mg of ephedrine will also be administered. Routine prophylaxis will be applied to prevent nausea and vomiting. Surgical incision will be permitted once the loss of pinprick sensation is confirmed bilaterally at the T6 dermatome. If patients experience discomfort during the procedure, a bolus of 0.5 mg/kg propofol and 0.25 mg/kg ketamine will be administered intravenously, consistent with routine practice. If these measures prove ineffective, the patient will be transitioned to general anesthesia and excluded from the study.

Following delivery, 100 IU of carbetocin will be administered as a uterotonic via graduated intravenous infusion. At the end of the procedure, 1000 mg of IV paracetamol will be administered for analgesic purposes. Supplemental postoperative analgesia will be provided via a bilateral transversus abdominis plane (TAP) block using 20 ml of 0.25% bupivacaine.

Monitoring and Data Collection

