The upper sensory level of anesthesia will be systematically assessed every two minutes along the midclavicular line using the loss of pinprick sensation. Additionally, the time to surgical incision, the sensory block level at the 30-minute mark, the application of Trendelenburg positioning, the administration of supplemental analgesia, and any transitions to general anesthesia will be recorded. Mean arterial pressure (MAP) and heart rate will be recorded at baseline and every 3 minutes thereafter, beginning 3 minutes after the spinal injection and continuing until the end of the surgical procedure. The occurrence of nausea and vomiting, along with the total amount of ephedrine administered, will be systematically documented. An attending nurse, blinded to the patients' group assignments, will assess Apgar scores at both 1 and 5 minutes post-delivery.

Statistical Analysis

A pre-study power analysis was performed using G*Power (v3.1.9.7; Franz Faul, Universität Kiel, Germany) based on the primary hypothesis defined as the rate of hypotension in each group. Using data from retrospective studies and assuming an effect size of 0.30, it was calculated that at least 69 patients per group (207 total) were required for an ANOVA test. This calculation provides a study power of 0.95 with a significance level (α) of 0.05.

Data will be analyzed using Analysis of Variance (ANOVA), the Kruskal-Wallis test, and Fisher's exact test, as appropriate. Bonferroni corrections will be applied for multiple comparisons. A p-value < 0.05 will be considered statistically significant. All statistical analyses will be performed using JAMOV version 2.6.19 for Windows.

References:

- 3-Šklebar I, Bujas T, Habek D. Spinal anaesthesia-induced hypotension in obstetrics: Prevention and therapy. *Acta Clin Croat* 2019;58(Suppl 1):90-5.

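### Hypotension is the only powered hypothesis, block adequacy has no defined role, and patients converted to general anesthesia are dropped, so less hypotension alone cannot show better dosing

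*Combined protocol and SAP*

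**What the plan says.** **Endpoint and size.** Statistical Analysis ties the power calculation to hypotension: it was "based on the primary hypothesis defined as the rate of hypotension in each group". The inputs are "assuming an effect size of 0.30", giving "at least 69 patients per group (207 total) were required for an ANOVA test", and "This calculation provides a study power of 0.95 with a significance level (α) of 0.05". The opening methods text sets the number of records: "The data of 285 patients who underwent routine procedures will be examined".

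**Hypotension.** Clinical Management gives a yes/no definition: "Hypotension, defined as a decrease in baseline systolic blood pressure of more than 30% or a systolic blood pressure below 90 mmHg".

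**Groups.** The opening methods text separates patients by dosing method: 0.2 mg per cm of C7-to-Tuffier length (VBU), 0.065 mg per cm of height (Height), or a height-and-weight chart (AD).

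**Block adequacy.** Monitoring and Data Collection has the sensory level tested every two minutes and notes the time to incision and the 30-minute level. It adds that "the application of Trendelenburg positioning, the administration of supplemental analgesia, and any transitions to general anesthesia will be recorded". None of these is called co-primary or key secondary, and none has a definition of failure. Clinical Management sets a condition for starting surgery: "Surgical incision will be permitted once the loss of pinprick sensation is confirmed bilaterally at the T6 dermatome". It also states that a patient whose discomfort is not relieved by the intravenous bolus is converted to general anesthesia and then leaves the study.

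**Tests.** ANOVA, Kruskal-Wallis and Fisher's exact test are listed for the data in general, with Bonferroni correction. No family of comparisons is named.

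**The concern.** One dose is expected to drive two outcomes. Less drug should mean less hypotension, and it may also mean a block that is slower, lower or in need of supplementation. That lower doses cause less hypotension is a clinical premise; it fits the study's rationale, but the documents do not quantify it. A formula could then look better on the primary endpoint because its average dose is lower, without fitting the dose to the patient any better.

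The exclusion makes this harder to see. Conversion to general anesthesia is the clearest failure of a spinal block. It is listed among the items recorded, yet the patient is removed, so the most informative adequacy events may not be counted against the formula that produced them. Those patients also leave the denominator for hypotension.

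At stake is the interpretation. A lower hypotension rate could be reported without the evidence needed to tell better individualisation from a smaller average dose.

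**Working it through.** **1. The plan's own figure.** For a one-way ANOVA with three groups, noncentrality λ = N × f², f = 0.30 (the index is not named; read as Cohen's f), α = 0.05 and power 0.95, the required N is 177 (59 per group), not 207. Power is 0.977 at 207 and 0.997 at 285. The stated size is larger than its own inputs require, so the mismatch is conservative. It is a separate matter and does not affect this point.

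**2. Can the formulas differ in mean dose?** Eligible heights run from 150 to 170 cm.

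| Height | Height rule (0.065 × height) | C7–Tuffier length giving the same VBU dose (dose ÷ 0.2) |
|---|---|---|
| 150 cm | 9.75 mg | 48.75 cm |
| 160 cm | 10.40 mg | 52.0 cm |
| 170 cm | 11.05 mg | 55.25 cm |

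Below the length in the last column the VBU rule gives less drug than the Height rule; above it, more. Each 5 cm changes the VBU dose by 5 × 0.2 = 1 mg. Expected lengths are not given. For assumed lengths of 40 to 60 cm the VBU dose is 8.0 to 12.0 mg, so the difference can go either way. The AD chart (Table 1) is not shown in the available text, so that group cannot be placed.

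**3. What could a 1 mg difference do? (Illustration; every input is assumed.)** Take 60% hypotension at the reference dose and a dose 1 mg lower. New logit = ln(0.60/0.40) − ln(OR) = 0.405 − ln(OR).

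- OR 1.3 per mg: 0.405 − 0.262 = 0.143, or 53.6% (6 points lower)
- OR 1.5 per mg: 0.405 − 0.405 = 0, or 50.0% (10 points lower)
- OR 2.0 per mg: 0.405 − 0.693 = −0.288, or 42.9% (17 points lower)

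**4. Would the listed tests reveal the matching loss of adequacy?** Pairwise power for two proportions (normal approximation, pooled variance under the null), with assumed rates of inadequate block:

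| Inadequate block | 95 per group, α 0.05 | 95 per group, α 0.05/3 | 69 per group, α 0.05 |
|---|---|---|---|
| 5% vs 10% | 26% | 14% | 20% |
| 5% vs 15% | 63% | 46% | 50% |
| 5% vs 20% | 88% | 77% | 77% |

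The 95 is 285 ÷ 3 and assumes equal groups. A large loss would probably be seen; a moderate or small one could easily be missed, so a non-significant result would not reassure. These figures also require that conversions be counted.

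**5. Precision of a reported difference.** For 5% vs 10% with 95 per group, SE = √[(0.05 × 0.95 + 0.10 × 0.90)/95] = 0.038. The 95% CI half-width is 1.96 × 0.038 = 7.5 points.

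**6. Would a formal non-inferiority gate be affordable?** n per group = (z₁₋α + z₀.₈₀)² × 2p(1 − p)/m², with one-sided α = 0.025, 80% power and equal true adequacy p:

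- p = 95%, m = 10 points: 7.849 × 0.095/0.01 = 74.6, so 75
- The same with Bonferroni over three pairs (α = 0.025/3, z = 2.394): 10.469 × 0.095/0.01 = 99.5, so 100
- p = 90%, m = 10 points: 7.849 × 0.18/0.01 = 141.3, so 142
- p = 95%, m = 5 points: 7.849 × 0.095/0.0025 = 298.3, so 299

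Against about 95 per group, only the first case fits.

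**The case against.** A single primary outcome with others recorded beside it is a common and legitimate design. The study is an observational comparison of methods already in routine use. Adequacy is measured in detail, nothing limits the listed tests to hypotension, and incision waits for a T6 block, which limits how far a weak block can go unnoticed.

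Most of this stands. A reader might infer that the plan judges success only on hypotension and will recommend whichever formula gives the least drug. The documents do not support that: they contain no rule for naming a method best, the general analysis sentence can cover adequacy, and no formula is shown to under-dose. The document's opening pages were not available either, so aims or secondary outcomes stated there cannot be ruled out.

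The objection does not remove two gaps. The T6 condition governs when surgery starts and is not an outcome; a weak block can still appear as delay, supplementation or conversion. And generic tests on recorded items do not restore the patients whom the plan removes.

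**Conclusion.** The point holds as a gap in interpretation, not as a fault in the choice of primary endpoint. In the visible text hypotension is the only primary and powered hypothesis, adequacy has no defined role, and the clearest block failures are excluded. A lower hypotension rate could therefore coexist with less adequate blocks without the plan requiring the two to be read together.

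The size cannot be derived from the documents. The 6-to-17-point illustration depends wholly on the assumed 60% rate, the odds ratios and a 1 mg difference, and the direction of any dose difference between formulas is unknown. The power figures depend on equal groups and assumed failure rates. The exclusion of converted patients needs no such assumption: it is in the text. This is a worthwhile, low-cost improvement.

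**What to change.** Keep hypotension as the primary endpoint, and change the analysis plan as follows.

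1. **Analysis set.** Keep patients converted to general anesthesia, analyse them in their dosing group and count them as block failures. Delete the exclusion, and state whether blood pressure after conversion counts towards hypotension. Clinical care is unaffected.
2. **Inadequate block.** Define it in advance as any of: T6 not reached by a time point fixed beforehand, supplemental analgesia given, or conversion to general anesthesia. The time point is needed because incision waits for T6. Report head-down tilt separately, because the plan does not provide for recording why it was used.
3. **Key secondary endpoint.** Name the proportion with an adequate block and no hypotension.
4. **Reporting.** For each pair of formulas give the difference and 95% CI for hypotension, inadequate block and the composite. Do not describe a formula as better dosing on hypotension alone.
5. **No formal non-inferiority gate.** The planned size supports one only under favourable assumptions.

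**Cost:** revised wording, two derived variables from items already recorded, and somewhat more analysis. Adequacy differences will be imprecise, and the final claim will be more cautious.

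### The stated ANOVA inputs give 177 patients, not 207; the sizing should instead rest on a test of proportions, and neither the effect size of 0.30 nor the total of 285 is explained

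*Combined protocol and SAP*

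**What the plan says.** The Statistical Analysis section says the G*Power calculation was "based on the primary hypothesis defined as the rate of hypotension in each group". It continues: "assuming an effect size of 0.30, it was calculated that at least 69 patients per group (207 total) were required for an ANOVA test". It then adds: "This calculation provides a study power of 0.95 with a significance level (α) of 0.05". The effect size is attributed to retrospective studies, but the section does not say whether 0.30 is Cohen's f or w, and it gives neither hypotension rates nor an allowance for losses.

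Clinical Management defines hypotension as a threshold event on systolic pressure, so each woman either has it or does not. The same section removes women converted to general anaesthesia from the study, without an expected rate.

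The unnumbered methods text at the start describes three dosing groups formed by the method used in routine practice. It gives a different total: "The data of 285 patients who underwent routine procedures will be examined". Planned group sizes are not given.

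The analysis list names ANOVA, Kruskal-Wallis and Fisher's exact test, to be used as appropriate. None is assigned to the primary endpoint.

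**The concern.** The paragraph gives everything needed to repeat the calculation: test, effect size, alpha, power and, from the methods text, three groups. Repeating it does not return the stated number. The calculation also uses a test of means for an endpoint that is a proportion, so 0.30 cannot be read as a difference in hypotension rates. The 285 women to be examined are not linked to the 207 said to be required.

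What is at stake is how the result will be read. A reader who meets a non-significant comparison will set it against the claimed power of 0.95. Without the rates behind 0.30, that reader cannot tell how large a difference the study was built to detect, or what power 285 patients give for a smaller one.

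**Working it through.** **Inputs from the documents.** Groups k = 3 (methods text). Effect size 0.30, alpha 0.05, power 0.95, test ANOVA, stated result 69 per group and 207 in total (Statistical Analysis). Patients to be examined: 285 (methods text). Equal groups are assumed throughout, because the plan gives no group sizes.

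**Step 1: the plan's own calculation.** For a one-way ANOVA, power = P(F′ > F_crit), where F′ is noncentral F with k − 1 = 2 and N − 3 degrees of freedom and noncentrality λ = N f².

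| N | λ = N × 0.09 | F_crit | Power |
|---|---|---|---|
| 174 | 15.66 | 3.049 | 0.949 |
| 177 | 15.93 | 3.048 | 0.953 |
| 207 | 18.63 | 3.040 | 0.977 |
| 285 | 25.65 | 3.028 | 0.997 |

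The smallest equal-group total reaching 0.95 is 177, or 59 per group. The stated 207 is 30 higher (30/177 = 17%), which is too much for rounding. For 207 to give power of about 0.95, f would have to be about 0.275 to 0.277.

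**Step 2: a test that fits the endpoint.** For a 3 × 2 table, power = P(χ′² > 5.991), where χ′² is noncentral chi-square with df = (3 − 1)(2 − 1) = 2 and λ = N w². Here 0.30 is read as w.

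- N = 171: λ = 15.39, power 0.949.
- N = 172: λ = 15.48, power 0.950. This is the required total (58 per group, 174, if groups are equal).
- N = 207: power 0.978.
- N = 285: power 0.997.

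**Step 3: what w = 0.30 means in rates.** If one group differs from two equal groups, w² = (2/9)d² / [p̄(1 − p̄)], where d is the difference and p̄ the overall rate. So d = 3w√[p̄(1 − p̄)] / √2. With w = 0.30, d is 0.29 at p̄ = 0.30, 0.32 at p̄ = 0.50 and 0.31 at p̄ = 0.60. This is one pattern among several; the documents do not say which was meant.

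**Step 4: a smaller difference, by assumption.** The documents give no rates, so these are illustrations: two groups at a baseline rate, one group 20 points lower, equal groups, df = 2.

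| Assumed rates | w | Power, N = 207 | Power, N = 285 |
|---|---|---|---|
| 30/30/10% | 0.223 | 0.83 | 0.93 |
| 40/40/20% | 0.200 | 0.73 | 0.87 |
| 50/50/30% | 0.190 | 0.69 | 0.83 |
| 60/60/40% | 0.189 | 0.68 | 0.82 |
| 70/70/50% | 0.196 | 0.71 | 0.85 |

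For 50/50/30%: p̄ = 1.3/3 = 0.433, w² = (2/9)(0.04)/(0.433 × 0.567) = 0.0362, and λ = 285 × 0.0362 = 10.3.

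**Step 5: 207 against 285.** 285 − 207 = 78. Reaching 285 from 207 through losses would take an allowance of 1 − 207/285 = 27.4%, and none is stated.

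**The case against.** The strongest reply is that nothing is lost. Both 207 and 285 exceed 177 and 172, so correcting the arithmetic lowers the minimum and leaves no shortfall at the stated effect. That stands, and it is why this is a reporting defect and not a study that is too small on its own terms. The choice of test family also moves the number little (177 against 172), and Fisher's exact test is already in the analysis list. The mismatch lies in the sizing and in the absence of a named primary test.

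An unstated allowance could also lie behind 207. A 15% loss applied to 58 per group gives 58/0.85 = 68.2, hence 69; and 172 × 1.20 = 206.4, hence 207. But the text presents 69 per group as what the ANOVA itself required, so these routes do not rescue the sentence as written.

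Three stronger readings are tempting, and the documents support none of them.

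- **That 285 contradicts 207.** It does not: 207 is stated as a minimum. What is missing is a reason for 285.
- **That a chi-square test with 4 degrees of freedom was run by mistake.** With w = 0.30 it does give exactly 207 (power 0.951). But the allowances above reach the same figure, so the match does not establish a cause.
- **That 0.30 is implausibly large, so the study is underpowered.** No hypotension rate appears anywhere in the documents, and the retrospective data cannot be seen. The rates in step 4 are illustrations; they show sensitivity and do not show that 0.30 is wrong.

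**Conclusion.** The point holds, and it should be fixed. The stated inputs give 177 patients, and 207 patients give power 0.977, so test, effect size, power and sample size do not belong together as written. For the yes/no primary endpoint the corresponding figure is 172 (w = 0.30, df = 2). The error is on the safe side at the stated effect.

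The more consequential gap is that neither 0.30 nor 285 is explained. A reader might infer that 0.95 is the power for any difference of interest. Under the assumed 20-point differences above, with equal groups, power is 0.68 to 0.83 at 207 and 0.82 to 0.93 at 285. Groups formed by routine practice may be unequal, which would lower power further when the smallest group is the one that differs: with an assumed split of 171/71/43 and 30% in the group of 43 against 50% elsewhere, it is 0.57 at 285.

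The 177, 172 and 0.977 rest only on the stated inputs, three groups and, for the ANOVA figures, equal group sizes. Everything below w = 0.30 rests on assumed rates.

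**What to change.** Rewrite the sample-size paragraph to do the following.

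1. Base the calculation on a three-group comparison of proportions with 2 degrees of freedom. Name the effect-size type and give the hypotension rates from the retrospective data that lead to it.
2. Replace 207 with the number that follows (172 in total for w = 0.30 at power 0.95), or state and apply the allowance that leads to 207.
3. Name the matching test of proportions, chi-square or Fisher's exact, as the primary analysis.
4. Explain 285 and state the power it gives: 0.997 at w = 0.30 with equal groups. Add the power for a smaller difference over a range of baseline rates, labelled as assumed, and note that it falls if the groups are unequal.

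Enrolling until each group reaches a quota is not advised. With groups set by routine practice it could take the study past 285 patients or past its December 2025 end date.

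The cost is one paragraph and a less favourable stated power for smaller differences. No added patients are needed.

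### Observational groups with no stated allocation rule are compared only with unadjusted tests, so any imbalance in body size or baseline pressure would be read as an effect of the dosing method.

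*Combined protocol and SAP*

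**What the plan says.** The unnumbered opening methods text sets the design: "an observational clinical study strategy will be followed in routine spinal anesthesia applications". On how patients come to be in one group or another it offers three statements:

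- "In our clinic, all three dose calculation systems are routinely used in spinal anesthesia for cesarean sections".
- "There was no pre-planning among the patients".
- After the procedures, "the results will be separated based on the dose of bupivacaine administered to the pregnant woman".

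It describes no randomisation, matching, stratification or selection rule. The only wording that suggests assignment concerns masking: "The patient and evaluator group assignments will be unknown".

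The three methods use different body measurements: vertebral length, height alone, or height and weight together. Entry is restricted by body size: "those weighing <50 kg or >110 kg, and those taller than 170 cm or shorter than 150 cm will not be included". Baseline blood pressure and heart rate are recorded. Under Clinical Management, hypotension is a fall of over 30% from baseline systolic pressure, or a systolic reading under 90 mmHg.

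The Statistical Analysis section makes the hypotension rate the subject of the primary hypothesis. On method it says "Data will be analyzed using Analysis of Variance (ANOVA), the Kruskal-Wallis test", followed by Fisher's exact test and Bonferroni correction. It mentions no covariates, regression model, propensity method or check of baseline balance.

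**The concern.** Without randomisation, nothing in the design makes the three groups comparable before injection. The listed tests are valid tests of the dosing method only if the groups are alike in everything else that affects hypotension. The plan does nothing to bring that about, to check it, or to correct for its absence.

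The risk is particular to this study in two ways. First, the methods are distinguished by the body measurements they use, so body size is an obvious candidate for a factor that differs between groups. Second, one limb of the hypotension definition is relative to baseline systolic pressure and the other is an absolute floor, so a baseline difference can feed directly into the endpoint.

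At stake is the study's main comparison. A significant result could reflect who received each method, and a null result could hide a real difference that an imbalance has cancelled.

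**Working it through.** **The plan's own figure.** The only figure in the Statistical Analysis section is 69 per group (207 in total) for an ANOVA with effect size 0.30, power 0.95 and α 0.05. Taking 0.30 as Cohen's f with three groups, the noncentral F calculation gives 59 per group (177), and 69 per group gives power 0.977. The stated number is not a shortfall, and the present point does not depend on it.

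**Inputs.** From the documents: 285 patients, three groups, Fisher's exact test, Bonferroni correction. Assumed, because the documents give no values: equal groups (285/3 = 95), hypotension risks by weight, the imbalance between groups, and no true effect of method. With three pairwise comparisons the Bonferroni level is 0.05/3 = 0.0167.

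**Illustration 1: one binary factor, two groups compared.** Crude rate = risk in other women + (risk in heavier women − risk in other women) × proportion heavier.

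- Larger imbalance, risks 60% and 35%, heavier 60% vs 20%: 0.35 + 0.25 × 0.60 = 0.50 and 0.35 + 0.25 × 0.20 = 0.40. The false difference is 10 points.
- Milder imbalance, risks 55% and 35%, heavier 60% vs 30%: 0.35 + 0.20 × 0.60 = 0.47 and 0.35 + 0.20 × 0.30 = 0.41. The false difference is 6 points.

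The rejection probability is the sum of the two binomial probabilities over all pairs of counts for which Fisher's two-sided p is at or below the level:

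| Crude rates | n per group | Level 0.05 | Level 0.05/3 |
|---|---|---|---|
| 50% vs 40% | 95 | 23% | 12% |
| 50% vs 40% | 69 | 17% | 9% |
| 47% vs 41% | 95 | 10% | 4% |

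Bonferroni correction lowers the rejection rate but leaves the 10- or 6-point bias in the estimate untouched. In the first scenario the corrected rate of 12% is about seven times its nominal 1.7%.

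**Illustration 2: one continuous factor, all three groups.** Simulation with no method effect, 50% hypotension at the covariate's centre, and group means of the covariate at −d, 0 and +d SD. The unadjusted test is a 3×2 chi-square at 0.05, standing in for Fisher's exact test. The adjusted test is a likelihood-ratio test from a logistic model containing the covariate.

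| d (SD) | Odds ratio per SD | Unadjusted, n = 95 | Unadjusted, n = 69 |
|---|---|---|---|
| 0 | 1.5 or 2.0 | about 5% | about 4% |
| 0.25 | 1.5 | 8% | 7% |
| 0.25 | 2.0 | 14% | 12% |
| 0.5 | 1.5 | 20% | 16% |
| 0.5 | 2.0 | 44% | 33% |

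The adjusted test stays at about 4–6% in every row. The unadjusted error under imbalance is higher at 95 than at 69 per group, so a larger sample does not help.

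**Group definition.** Two formulas can give the same dose. At a height of 160 cm the height formula gives 160 × 0.065 = 10.4 mg. The vertebral-length formula gives the same dose at 10.4/0.2 = 52 cm. The documents give no distribution of vertebral lengths, so how often this would happen is unknown. It does mean that dose alone need not identify the method.

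**The case against.** The case on the other side has real substance, though none of it supplies the missing adjustment.

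- **Method choice.** A reader might infer that clinicians pick the method by height, weight or condition. The documents do not say so. That height and weight set the dose within a method does not show that they decide which method is used, and the remark about no pre-planning could even mean that patient features played no part. What stands is only that the choice is unexplained, so imbalance is neither shown nor excluded.
- **Restriction.** A reader might infer that the comparison has no protection at all. That goes too far. The height and weight limits, and the exclusion of ASA III–IV, preeclampsia, diabetes, cardiorespiratory problems and emergencies, are a recognised partial control. They still leave 50–110 kg and 150–170 cm, within which groups can differ.
- **Validity of the p-values.** It is tempting to say that unadjusted p-values never test the dosing method. With balanced groups the error is about 4–5%, so the bias is conditional.
- **Size.** An uncorrected two-group normal-approximation test gives 28% (95 per group) and 22% (69 per group) in the larger scenario, and 13% (95 per group) in the milder one. Those figures overstate the matter, because the plan names Fisher's exact test and Bonferroni correction. Even the lower figures rest on assumed risks and imbalances, and a 60% vs 20% split is large.
- **Design.** An observational comparison is legitimate, and randomising would make this a different study. The fault lies in the analysis that accompanies the design.
- **Grouping.** The group descriptions that follow the sentence on separating by dose are written as formulas, so the method is probably what is meant. The wording should say so.

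**Conclusion.** The concern holds in conditional form. The plan states no allocation rule and forms groups afterwards, yet the primary hypotension comparison has only unadjusted tests. If the groups differ in height, weight or baseline pressure, the comparison is biased, and neither the entry limits, the masking nor Bonferroni correction removes that bias.

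The size cannot be known from the documents. Under the assumed scenarios in the working, with 95 per group, false differences of 6 to 10 points arise. Pairwise Fisher rejection is about 10–23% at 0.05 and about 4–12% at 0.05/3. These figures show what moderate to large imbalance would do. They do not predict what this study will find. The gap should be closed before the data are analysed, because it affects the main comparison and covariates chosen after seeing results invite selective adjustment.

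**What to change.** Required changes to the Statistical Analysis section and the opening methods text:

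1. Make the primary analysis a prespecified logistic regression of hypotension on dosing method, with height, weight, baseline systolic pressure and baseline heart rate as covariates. Report adjusted risk differences with 95% confidence intervals.
2. Do not adjust for the dose given. It lies on the path from method to outcome.
3. Define groups by the method used rather than by the dose administered.
4. State how the method is chosen for each patient, and report baseline balance by group.
5. Keep the unadjusted tests as descriptive, and word conclusions as associations.

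Optional: propensity-score overlap weighting as a sensitivity analysis, and replacing the group-assignment wording with a reference to the method used.

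Cost: a revised analysis section, a little more analysis work, and possibly wider intervals. No new data are needed: baseline pressure and heart rate are already recorded, and height and weight are needed to apply the entry limits. At an assumed hypotension rate of 40% there would be 0.40 × 285 = 114 events. The model has six coefficients besides the intercept (two for method, four covariates), which gives 114/6 = 19 events per coefficient.
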